7.1.6.1. Calculation of Treatment Exposure

Treatment exposure will be calculated as follows, for SEL and placebo respectively:

- SEL: Total exposure (Patient Year) is calculated as the sum of Run-in SEL and Randomized SEL exposure time (in years) for all subjects who have been exposed to Run-in SEL and/or Randomized SEL in the Safety Analysis Set, starting from the first dosing date of Run-in SEL to the last dosing date of SEL (Run-in SEL or Randomized SEL).

In other words,

Total SEL Exposure

$$\begin{aligned}
 &= \sum_{i \in \{\text{Subjects randomized to SEL}\}} \text{Ex}(\text{first dose of Runin SEL to last dose of Randomized SEL})_i \\
 &+ \sum_{i \in \{\text{Subjects randomized to Placebo}\}} \text{Ex}(\text{first dose of Runin SEL to last dose of Runin SEL})_i \\
 &+ \sum_{i \in \{\text{Subjects not randomized}\}} \text{Ex}(\text{first dose of Runin SEL to last dose of Runin SEL})_i
 \end{aligned}$$

- Placebo: Total exposure (Patient Year) is calculated as the sum of Randomized placebo exposure time (in years) for all subjects who exposed to Randomized placebo in the Safety Analysis Set, starting from Study Day 1 to the last dosing date of Randomized placebo.

In other words,

Total Placebo Exposure

$$= \sum_{i \in \{\text{Subjects randomized to Placebo}\}} \text{Ex}(\text{first dose of Randomized Placebo to last dose of Randomized Placebo})_i$$

7.1.6.2. Calculation of Exposure-Adjusted AE Incidence Rate

EAIR for AEs will be calculated as follows for SEL and placebo exposure periods, respectively:

$$\begin{aligned}
 &EAIR(SEL) \\
 &= \frac{\text{\# of Subjects who experienced at least 1 TEAE of interest to SEL exposure}}{\text{Total SEL Exposure}}
 \end{aligned}$$

$$\begin{aligned}
 &EAIR(Placebo) \\
 &= \frac{\text{\# of Subjects who experienced at least 1 TEAE of interest to Placebo exposure}}{\text{Total Placebo Exposure}}
 \end{aligned}$$

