7.1.5. Treatment-Emergent Adverse Events

7.1.5.1. Definition of Treatment-Emergent Adverse Events

Treatment-emergent adverse events (TEAEs) are defined as follows for SEL and placebo exposures, respectively.

- SEL exposure: TEAEs are defined as 1 or both of the following:
 - Any AEs with an onset date on or after the Run-in SEL start date and no later than 30 days after permanent discontinuation of SEL
 - Any AEs leading to premature discontinuation of SEL

- Placebo exposure: TEAEs are defined as any AEs with an onset date on or after Study Day 31 (30 days after the Randomized placebo start date) and no later than 30 days after permanent discontinuation of Randomized placebo

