7.1.6.3. Summaries of Exposure-Adjusted AE Incidence Rate

A brief, high-level summary of the number of subjects who experienced at least 1 TEAE in the categories described below will be provided by exposure type (SEL or placebo) and overall. EAIRs (per 100 Patient Years) will also be presented. All deaths observed in the study, as well as EAIRs per 100 Patient Years will also be included in this summary by exposure type (SEL or placebo) and overall.

The number subjects who experienced at least 1 TEAE in the AE categories described below will be provided and summarized by SOC, PT, by exposure type (SEL or placebo) and overall. EAIRs (per 100 Patient Years) for AEs in these categories will also be provided.

- TEAEs
- TEAEs with Grade 3 or higher
- TE treatment-related AEs
- TE treatment-related AEs with Grade 3 or higher
- TE SAEs
- TE treatment-related SAEs
- TEAEs leading to premature discontinuation of study drug
- TEAEs leading to temporary interruption of study drug
- TEAEs leading to Death

Multiple events will be counted only once per subject per exposure type in each summary. Adverse events will be summarized and listed first in alphabetic order of SOC, and then by PT in descending order of total frequency within each SOC. For summaries by severity grade, the most severe grade will be used for those AEs that occurred more than once in an individual subject during one exposure type (SEL or placebo) during the study.

In addition to the above summary tables, all TEAEs, TE SAEs, TE treatment-related AEs, and TE treatment-related SAEs will be summarized by PT only, in descending order of total frequency.

In addition, data listings will be provided for the following in the All Enrolled Analysis Set:

- All AEs, indicating whether the event is treatment emergent
- All AEs of Grade 3 or above

- All SAEs
- All Deaths
- All AEs leading to premature discontinuation of study drug
- All AEs leading to temporary interruption of study drug

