7.2.2.3. Summaries of Laboratory Abnormalities

Laboratory data that are categorical will be summarized using the number and percentage of subjects in the study with the given response at Baseline and each scheduled postbaseline visit.

The following summaries (number and EAIR per 100 Patient Years) for treatment-emergent central laboratory abnormalities will be provided by lab test and exposure type (SEL or placebo); subjects will be categorized according to the most severe postbaseline abnormality grade for a given lab test:

- Treatment-emergent laboratory abnormalities
- Treatment-emergent Grade 3 or 4 laboratory abnormalities
- Treatment-emergent marked laboratory abnormalities

EAIR for treatment-emergent laboratory abnormalities will be calculated in the same manner as EAIR for TEAEs (Section 7.1.6.2).

A by-subject listing of treatment-emergent Grade 3 or 4 laboratory abnormalities will be provided by subject ID number and visit in chronological order. This listing will include all test results that were collected throughout the study for the lab test of interest, with all applicable severity grades displayed.

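### The exposure-adjusted AE rate keeps time after the first event in its denominator, so rates for very common categories come out far too low, while mismatched event windows distort the SEL/placebo comparison the other way

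*SAP*

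**What the plan says.** **Numerator.** SAP 7.1.6.2 takes, for SEL, the number of "Subjects who experienced at least 1 TEAE of interest to SEL exposure", and the matching count for placebo. SAP 7.1.6.3 adds: "Multiple events will be counted only once per subject per exposure type in each summary".

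**Denominator.** SAP 7.1.6.1 sums dosing time. For SEL it runs "starting from the first dosing date of Run-in SEL to the last dosing date of SEL", over everyone dosed with Run-in SEL, including placebo-randomized and non-randomized subjects. For placebo it runs "starting from Study Day 1 to the last dosing date of Randomized placebo". Neither is cut at the first event.

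**Event windows (SAP 7.1.5.1).** SEL events count from the first Run-in SEL dose and "no later than 30 days after permanent discontinuation of SEL". Placebo events count only from Study Day 31, to 30 days after the last placebo dose.

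**Reach.** SAP 7.2.2.3 states: "EAIR for treatment-emergent laboratory abnormalities will be calculated in the same manner as EAIR for TEAEs". SAP 7.2.3 also reports liver-test abnormalities as EAIRs.

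**Contrast.** For the kidney event rate, SAP 6.2.2.2 ends each subject's follow-up at the event of interest if that comes first.

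**The concern.** A first-event count needs a denominator of time during which a first event can still occur. Once a subject has had the event, later dosing time cannot add to the numerator. Leaving it in turns the rate into a saturating proportion divided by follow-up: for a common event the numerator stops growing and the denominator does not. The same hazard then gives a lower rate in a longer trial.

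The two columns also saturate differently. The SEL column mixes run-in-only exposures of about five weeks with exposures of a year or more. The placebo column holds only the long ones.

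The windows add a second mismatch inside the same fraction. SEL events in the 30 days after the last dose are counted with no exposure added. This includes events in the first 30 days of randomized placebo, which count as SEL events while that time counts as placebo exposure. These rates are the planned AE summaries, set side by side by exposure type, and readers will compare them.

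**Working it through.** The documents give no EAIR or rate ratio, so there is no stated figure to reproduce.

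**Inputs from the documents**
- Phase 2 placebo proportions over 48 weeks (0.92 years): any AE 83.5% (Protocol Table 1-3), Grade 3–4 laboratory abnormality 51.8% (Table 1-6), SAE 18.8% (Table 1-5), most frequent placebo preferred term 10.6% (Table 1-4).
- 150 per arm (SAP 1.3).
- Run-in SEL of 28–42 days from the visit windows in the protocol synopsis; 35 days used (T0 = 0.096 years).
- Windows from SAP 7.1.5.1 (w = 30 days = 0.082 years).

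**Assumptions**
- Constant hazards.
- Mean randomized exposure T = 0.92, 1.35 or 1.7 years.
- 30 non-randomized subjects, so 180 with run-in SEL only.
- Follow-up for 30 days after the last dose.

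**Step 1: level.** First-event hazard λ = −ln(1 − p)/0.92. Planned placebo rate = (1 − exp(−λT))/T. The placebo window (Day 31 to last dose + 30 days) also has length T, so the windows leave this figure unchanged. For any AE, λ = −ln(0.165)/0.92 = 1.96. At T = 0.92 the planned rate is 0.835/0.92 = 0.91. At T = 1.7 it is 0.964/1.7 = 0.57.

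| Category | True rate per 100 PY | Planned placebo rate, T = 0.92 to 1.7 |
|---|---|---|
| Any AE | 196 | 91 down to 57 |
| Grade 3–4 lab | 79 | 56 down to 44 |
| SAE | 23 | 20 down to 19 |

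For the 10.6% preferred term over 48 weeks, the rate is 5% low on placebo, and 8% low at 1.5 times the placebo hazard.

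**Step 2: SEL/placebo ratio.** Let h be the SEL hazard and g the hazard in the 30 days after SEL, set to h or to λ.

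SEL rate = {150[1 − exp(−h(T + T0) − g·w)] + 180[1 − exp(−h·T0 − g·w)]} / [150(T + T0) + 180·T0]

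Example: any AE, T = 0.92, h = 1.5λ = 2.94, g = h. The numerator is 144.0 + 73.3 = 217.3 and the denominator 169.6, giving 1.28. Divided by 0.91, the ratio is 1.41. Setting w = 0 isolates the denominator effect.

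| Category | True 1.50, denominator effect only | True 1.50, SAP windows | True 1.00, SAP windows |
|---|---|---|---|
| Any AE | 1.19–1.21 | 1.31–1.41 | 1.20–1.23 |
| Grade 3–4 lab | 1.22–1.31 | 1.31–1.51 | 1.12–1.16 |
| SAE | 1.38–1.43 | 1.47–1.65 | 1.10–1.16 |
| 10.6% preferred term | 1.43–1.46 | 1.52–1.69 | 1.09–1.16 |

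A wider grid (0–100 non-randomized subjects, 48–120 weeks) gives 1.07–1.35 when there is no effect. A simulation with the 22.8% Phase 2 drug discontinuation and an assumed 48–130 week cut-off reads a true 1.50 as 1.39–1.50 for placebo incidence of 40% or more, and 1.52–1.63 for 18.8% or less.

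**Step 3: candidate corrections, any AE, true 1.50.**
- *Stop dosing time at the first event, windows unchanged.* The SEL denominator becomes the sum of (1 − exp(−hL))/h over subjects with dosing time L. The placebo denominator per subject becomes w + (1 − exp(−λ(T − w)))/λ. The ratio reads about 2.0, because the window mismatch now acts on a much smaller denominator.
- *Stop at the first event and match time at risk to the window.* SEL time at risk per subject becomes (1 − exp(−hL))/h + exp(−hL)(1 − exp(−g·w))/g. The ratio reads 1.50 if the SEL hazard persists through the 30 days, and about 1.43 if it reverts to the placebo level.

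**The case against.** The planned quantity is openly defined, and the SAP never says it estimates a first-event hazard. It plans no SEL/placebo rate ratio and no safety test. Subject counts stand beside the EAIRs, AEs of special interest are given as number and percentage (SAP 7.1.7), and all AEs are listed. Most rows are preferred terms, where the effect on level is small. The calculation assumes constant hazards, a mean exposure and a number of non-randomized subjects that the documents do not give.

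Much of this stands. No formal inference depends on the formula, the level error is large only for broad, common categories, and the ratios are illustrations of how two columns would look side by side. It does not rescue the rate as a summary: it falls with follow-up under a constant hazard, and the SAP already handles the same issue for kidney events by stopping at the event.

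A reader might also infer that the formula generally shrinks real SEL excesses toward 1, so that a true 50% excess shows as only 20–40%. The documents do not support that. It describes the denominator effect with event windows matched to exposure, which is not how SAP 7.1.5.1 defines them. With the planned windows, SAEs read 1.47–1.65 and the 10.6% preferred term 1.52–1.69, at or above the truth in most scenarios. A SEL excess also appears when there is none.

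**Conclusion.** The concern holds for the level of the rates. EAIRs for very common categories are far too low and depend on follow-up length: any AE by more than half, Grade 3–4 laboratory abnormalities by about 30–45%. SAEs are modestly affected and single preferred terms little.

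For the comparison, the denominator and the event windows err in opposite directions, and their balance shifts with event frequency and follow-up. The net ratio may be too low or too high, and no effect reads about 1.1–1.2 in the main scenarios. Partial cancellation of this kind does not make the tables interpretable.

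The reading of the formula is certain, since it rests on the SAP text. The sizes are conditional on the stated assumptions, and the ratios more so than the levels, because they also depend on the hazard in the 30 days after SEL. The change should be made.

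**What to change.** For each event type and exposure type, define the EAIR as subjects with the event divided by time at risk, where time at risk:
- starts and ends with the TEAE window in SAP 7.1.5.1: for SEL, first Run-in SEL dose to last SEL dose + 30 days; for placebo, Study Day 31 to last placebo dose + 30 days; each limited by the end of follow-up; and
- stops at the onset of the first such event.

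Make both changes in one edit. Apply the same rule in 7.2.2.3 and 7.2.3. The planned rate can stay as a supplementary column.

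The cost is SAP text and programming: one denominator per event term and exposure type in place of one common denominator. A date rule for incomplete onset dates is also needed, since 7.1.5.2 settles only whether such an event is treatment-emergent. No new data are needed: AE onset and dosing dates are already collected.

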7.1.6.3. Summaries of Exposure-Adjusted AE Incidence Rate

A brief, high-level summary of the number of subjects who experienced at least 1 TEAE in the categories described below will be provided by exposure type (SEL or placebo) and overall. EAIRs (per 100 Patient Years) will also be presented. All deaths observed in the study, as well as EAIRs per 100 Patient Years will also be included in this summary by exposure type (SEL or placebo) and overall.

The number subjects who experienced at least 1 TEAE in the AE categories described below will be provided and summarized by SOC, PT, by exposure type (SEL or placebo) and overall. EAIRs (per 100 Patient Years) for AEs in these categories will also be provided.

- TEAEs
- TEAEs with Grade 3 or higher
- TE treatment-related AEs
- TE treatment-related AEs with Grade 3 or higher
- TE SAEs
- TE treatment-related SAEs
- TEAEs leading to premature discontinuation of study drug
- TEAEs leading to temporary interruption of study drug
- TEAEs leading to Death

Multiple events will be counted only once per subject per exposure type in each summary. Adverse events will be summarized and listed first in alphabetic order of SOC, and then by PT in descending order of total frequency within each SOC. For summaries by severity grade, the most severe grade will be used for those AEs that occurred more than once in an individual subject during one exposure type (SEL or placebo) during the study.

In addition to the above summary tables, all TEAEs, TE SAEs, TE treatment-related AEs, and TE treatment-related SAEs will be summarized by PT only, in descending order of total frequency.

In addition, data listings will be provided for the following in the All Enrolled Analysis Set:

- All AEs, indicating whether the event is treatment emergent
- All AEs of Grade 3 or above

- All SAEs
- All Deaths
- All AEs leading to premature discontinuation of study drug
- All AEs leading to temporary interruption of study drug

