1.2.3.2.4. Safety Results

Table 1-3 presents the overall summary of AEs by treatment group. Overall, 80.8% of subjects experienced an AE: 83.5% in the placebo group and 79.8% in the pooled SEL group (79.0%, 84.5%, and 75.9% for SEL 2, 6, and 18, respectively). Adverse events related to study drug occurred in 9.4% (8 subjects) in the placebo group and 12.5% (31 subjects) in the pooled SEL group (8.6%, 11.9%, and 16.9% for SEL 2, 6, and 18 mg, respectively). Adverse events leading to study drug discontinuation occurred in 9.4% (8 subjects) in the placebo group compared with 12.1% (30 subjects) in the pooled SEL group (8.6%, 13.1%, and 14.5% for SEL 2, 6, and 18 mg, respectively). Overall, 4 deaths occurred (1.2%), with a frequency of 1.2% in the placebo group and 1.2% in the pooled SEL group (1.2%, 1.2%, and 1.2% for SEL 2, 6, and 18 mg, respectively). Three of the deaths were nontreatment emergent, i.e., occurred more than 30 days after the last dose of study drug.

Table 1-3. GS-US-223-1015: Overall Summary of Adverse Events (Safety Analysis Set)

Number (%) of Subjects With Any	SEL 2 mg (N = 81)	SEL 6 mg (N = 84)	SEL 18 mg (N = 83)	SEL Pooled (N = 248)	Placebo (N = 85)
AE	64 (79.0%)	71 (84.5%)	63 (75.9%)	198 (79.8%)	71 (83.5%)
Grade \geq 3 AE	21 (25.9%)	20 (23.8%)	21 (25.3%)	62 (25.0%)	15 (17.6%)
AE Related to Study Drug	7 (8.6%)	10 (11.9%)	14 (16.9%)	31 (12.5%)	8 (9.4%)
Grade \geq 3 AE Related to Study Drug	0	3 (3.6%)	0	3 (1.2%)	1 (1.2%)
SAE	24 (29.6%)	20 (23.8%)	20 (24.1%)	64 (25.8%)	16 (18.8%)
SAE Related to Study Drug	0	2 (2.4%)	0	2 (0.8%)	1 (1.2%)
AE Leading to Temporary Interruption of Study Drug	14 (17.3%)	8 (9.5%)	10 (12.0%)	32 (12.9%)	7 (8.2%)
AE Leading to Study Drug Discontinuation	7 (8.6%)	11 (13.1%)	12 (14.5%)	30 (12.1%)	8 (9.4%)
AE Leading to Death	0	1 (1.2%)	0	1 (0.4%)	0
All Deaths During Study	1 (1.2%)	1 (1.2%)	1 (1.2%)	3 (1.2%)	1 (1.2%)

Adverse events were mapped according to MedDRA Version 19
Treatment-emergent AEs are those started on or after first study dose date up to and including 30 days after permanent discontinuation, or led to premature study drug discontinuation
Toxicity grades (1=Mild, 2=Moderate, 3=Severe, 4=Life-Threatening, 5=Death) were from modified CTCAE Version 4.03

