6.7.3. Remote Assessments

Subjects who have permanently discontinued study drug, reached kidney failure, or are no longer able to continue to attend clinic visits in-person, and **have not withdrawn full consent** will be asked to continue study participation through remote contact, without in-clinic study visits. Subjects will be contacted approximately every 24 weeks until the global study end date. At a minimum, subjects will be contacted at the global study end date.

Subjects will be contacted via telephone, email, or other contact methods through friends or family. Details regarding discussions via telephone, email, or other contact must be properly documented by the site in the source records, including the responses from the subject. The investigator will make every effort to contact the subject or a close relative or caretaker by phone to collect information. The investigator should show due diligence by documenting in the source documents steps taken to contact the subject (e.g., dates of phone calls, registered letters, etc.).

Follow-up for survival, kidney outcomes, and safety will continue until reasons listed in protocol Section 3.5 are met or until the global study end date.

Information gathered will include:

- Survival status
- Death details, if applicable
- Receipt of kidney transplant
- Dialysis initiation post study drug discontinuation
- AE and SAE collection per protocol Section 7

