7. SAFETY ANALYSES

Unless otherwise specified, summaries of safety data will be provided for the Safety Analysis Set and will include data collected up to the last dose of study drug plus 30 days.

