7.1.6. Summaries of Adverse Events and Deaths

Exposure-adjusted treatment-emergent AE incidence rates will be summarized based on the Safety Analysis Set, by exposure type (SEL or placebo) and overall. SEL exposure includes Run-in SEL exposure and Randomized SEL exposure.

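### SAP 7.1.6.3 gives an exposure-adjusted rate for all deaths in the study, but the only exposure denominator defined stops at the last dose

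*SAP*

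**What the plan says.** **Numerator.** SAP 7.1.6.3, on the high-level adverse event summary: "All deaths observed in the study, as well as EAIRs per 100 Patient Years will also be included in this summary by exposure type". The safety default in SAP Section 7 is that summaries "will include data collected up to the last dose of study drug plus 30 days", but that holds only unless otherwise specified, and asking for every death in the study specifies otherwise. Treatment-emergent AEs leading to death are a separate category in 7.1.6.3, so the all-deaths row is not meant to be limited to treatment-emergent deaths.

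**Denominator.** SAP 7.1.6.2 opens: "EAIR for AEs will be calculated as follows for SEL and placebo exposure periods, respectively". Each formula divides subjects with a treatment-emergent event by total exposure. No other EAIR formula is given. Under 7.1.6.1 placebo exposure is counted "starting from Study Day 1 to the last dosing date of Randomized placebo", and SEL exposure from the first run-in SEL dose to the last SEL dose. SAP 7.1.6 adds: "SEL exposure includes Run-in SEL exposure and Randomized SEL exposure". The SEL total therefore includes run-in time from subjects later randomized to placebo and from subjects never randomized.

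**Follow-up.** Protocol 6.7.3, for subjects off drug or in kidney failure who have not withdrawn full consent: "Follow-up for survival, kidney outcomes, and safety will continue until reasons listed in protocol Section 3.5 are met or until the global study end date". Protocol 6.5 has subjects who reach kidney failure stop drug and remain on study by remote contact.

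**The concern.** A person-time rate needs its events and its time at risk to cover the same period. Here the numerator has no end before study end, while the denominator stops at the last dose. The result is neither an on-treatment death rate nor a follow-up death rate. It cannot be compared with the treatment-emergent rows beside it, and it rises with drug stopping even when mortality does not change.

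Assignment is also open. SAP 3.2 groups subjects and events by exposure, but no rule covers a death long after the last dose. Nor does the all-deaths row say where a placebo-arm death before Study Day 31 goes, although the placebo treatment-emergent window in 7.1.5.1 starts only then. Mortality is the row of the safety overview that readers will look at first.

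**Working it through.** The documents state no mortality rate, so there is no figure of the plan's own to reproduce.

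**Inputs**
- Drug stopping by Week 48 in the completed Phase 2 DKD study (Protocol 1.2.3.2.2): placebo 19/85 = 22.4%; SEL 18 mg 28.9%. These stand in for this trial's unknown rates.
- 150 subjects per arm (SAP 1.3).
- Horizons T of 48 weeks (minimum treatment after randomization) and 84 weeks (primary endpoint).
- Assumed: constant stopping hazard, complete survival follow-up to T, and death shortening neither time.

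**Step 1. Randomized-period time**

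h = −ln(1 − p)/48 per week; mean on-drug time = (1 − exp(−hT))/h; overstatement factor = T ÷ mean on-drug time.

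| T | Arm | On-drug weeks | Share of T | Factor |
|---|---|---|---|---|
| 48 | Placebo | 42.4 | 88.3% | 1.13 |
| 48 | SEL 18 mg | 40.7 | 84.7% | 1.18 |
| 84 | Placebo | 67.8 | 80.8% | 1.24 |
| 84 | SEL 18 mg | 63.3 | 75.3% | 1.33 |

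**Step 2. In rates**

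Take T = 84 weeks and an assumed true mortality of 2.0 per 100 patient-years in both arms. Follow-up is 150 × 84/52.18 = 241.5 patient-years per arm, giving 4.83 expected deaths per arm. On-drug time is 195.0 (placebo) and 181.8 (SEL) patient-years.
- All deaths over on-drug time: 4.83/195.0 = 2.48 and 4.83/181.8 = 2.66 per 100.
- All deaths over follow-up time: 2.00 in both arms.

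The factor does not depend on the mortality pattern. If mortality off drug is assumed to be twice that on drug, the rates are 2.95 against 2.38 (placebo) and 3.31 against 2.49 (SEL), again 1.24 and 1.33.

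**Step 3. Run-in time in the SEL column**

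The SAP's table is by exposure type, so run-in SEL time enters the SEL denominator. At T = 84 weeks, randomized SEL time is 150 × 63.3 ≈ 9,490 weeks and randomized follow-up is 150 × 84 = 12,600 weeks. The ratios below divide the SEL factor by placebo's 1.24, with equal mortality after randomization.
- No run-in time counted: 1.33/1.24 = 1.07.
- 4 weeks in 300 subjects (1,200 weeks), same mortality in the run-in: (12,600 + 1,200)/(9,490 + 1,200) = 1.29; ratio 1.04.
- Same 1,200 weeks, no deaths in the run-in: 12,600/10,690 = 1.18; ratio 0.95.
- 6 weeks in 360 subjects (2,160 weeks), no deaths in the run-in: 12,600/11,650 = 1.08; ratio 0.87.

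The run-in durations and the 60 run-in failures are assumptions. With equal stopping in both arms (22.4%) and the same mortality in the run-in, the SEL factor is 1.20 to 1.21 against 1.24 for placebo.

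**The case against.** **The denominator for deaths is inferred.** SAP 7.1.6.2 defines the EAIR for AEs, with treatment-emergent events on top, and gives no formula for deaths. One could call this missing detail only. That is fair as to certainty, but the section offers no other exposure denominator. Followed as written, the row is mismatched; on any other reading it is undefined. Either way the SAP needs new wording.

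**A reader can already separate the deaths.** Treatment-emergent AEs leading to death have their own EAIR, and a listing of all deaths is planned. This limits the harm but does not correct the printed rate.

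**Stronger readings that the documents do not support**
- A reader might infer a bias against SEL, since more subjects stopped SEL 18 mg than placebo in Phase 2. The run-in pooling can reverse the direction, as Step 3 shows. The Phase 2 difference is itself weak (24/83 against 19/85, Fisher p = 0.38; pooled SEL was 23.0%). In this trial, subjects who stop permanently in the active run-in are not randomized.
- A reader might infer a fourfold overstatement from the Phase 2 report: "Three of the deaths were nontreatment emergent, i.e., occurred more than 30 days after the last dose of study drug", out of four in all. That compares two numerators and is not a denominator error. It rests on four deaths (3/4, exact 95% CI 19% to 99%). It shows only that late deaths occur.
- A reader might infer that everyone is followed for survival to study end. Protocol 3.5 and 6.7.3 allow exit by full consent withdrawal, loss to follow-up and other routes. In Phase 2, 3.5% of placebo and 5.2% of pooled SEL subjects stopped drug by withdrawing consent. The Step 1 factors are therefore upper-end at those stopping rates.

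**Conclusion.** The concern stands as a numerator-denominator mismatch in one safety row, together with an unstated rule for assigning late deaths. Whenever deaths are followed off drug, all deaths over randomized-period on-drug time exceed the follow-up rate. The size is illustrative and rests on Phase 2 stopping, a constant hazard and complete survival follow-up: up to 13% (placebo) and 18% (SEL) at 48 weeks, and 24% and 33% at 84 weeks. In the table as specified, the SEL figure is diluted by run-in time. The SEL-to-placebo ratio at equal mortality could therefore lie on either side of 1, about 0.87 to 1.07 at 84 weeks under the assumptions shown. No bias for or against SEL is established.

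**What to change.** In SAP 7.1.6.3:
1. Remove the EAIR for all deaths by exposure type.
2. Report all deaths by randomized arm as number, percentage and rate per 100 patient-years, with time from randomization to death or last date known alive. SAP 6.2.2.2 already uses follow-up time from randomization for the kidney event rate. List deaths before randomization, or in subjects never randomized, separately.
3. Keep treatment-emergent AEs leading to death by exposure type, as already planned, but match the denominator to the counting window in 7.1.5.1: through last dose plus 30 days in both columns, and from Study Day 31 for placebo. Leaving the 7.1.6.1 exposure unchanged would keep a smaller mismatch of the same kind.

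The cost is SAP wording and one derived date, the last date known alive, from survival status already collected under Protocol 6.7.3. The stated overall death rates will be lower, which should be explained where they are reported.
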